4.2.2 Priority of Analyses

For each endpoint, one analysis will be identified as the “main” analysis of its evaluation. These analyses will be the basis upon which that endpoint will be evaluated. No formal hypothesis testing methods will be used.

Additional analyses of the information used in the main analysis such as subsets, covariate adjustments, and sensitivity analyses may be included in this analysis plan or added to the study report as needed. Such additional analyses may be added as separate tables/figures or have their results appended to the presentation of the main analysis and may also be presented in abbreviated forms.

4.2.3 Continuous Data

Continuous data will be summarized in terms of the mean, standard deviation, median, minimum, maximum, and number of observations, unless otherwise stated.

Continuous data that are expected to be skewed will be presented in terms of the maximum, upper quartile, median, lower quartile, minimum and number of observations. The minimum and maximum will be reported to the same number of decimal places as the raw data recorded in the database. The

mean, median, confidence intervals, lower quartile, and upper quartile will be reported to one more decimal place than the raw data recorded in the database. The SD will be reported to two more decimal places than the raw data recorded in the database. In general, the maximum number of decimal places reported shall be four for any summary statistic.

4.2.4 Categorical Data

Unless otherwise specified for a given analysis, categorical data will be presented by the following rules. Categorical data not broken out by time (e.g., AE incidence) will be summarized in terms of the number of participants in the appropriate analysis set (n), frequency counts, and percentages. Categorical data broken out by time (e.g., ECOG PS by visit) will be summarized in terms of the number of participants providing data at the relevant time point (n), frequency counts and percentages. Any planned collapsing of categories will be detailed in the relevant section of this SAP as well as specifications for the data displays.

Percentages will be presented to one decimal place. Percentages will not be presented for zero counts. Percentages will be calculated using n as the denominator as described above.

Changes from baseline in categorical data will be summarized using shift tables where appropriate.

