4. STUDY DESIGN

4.1. Overall Design

This is a multicenter, single-arm, open-label study to evaluate the safety and efficacy of lerociclib administered in combination with standard endocrine therapy in female or male participants with HR+/HER2- mBC.

The study population will consist of newly diagnosed, treatment-naïve participants with HR+/HER2- mBC (collectively referred to as the first-line, or 1L, population) and participants with HR+/HER2- mBC who have already progressed on first-line endocrine therapy such as tamoxifen, anastrozole, or letrozole (collectively referred to as the second-line, or 2L, population).

Approximately 100 participants will be enrolled and dosed in the study, with approximately 50 participants enrolled and dosed for each line of therapy (1L or 2L). All premenopausal or perimenopausal female participants, and all male participants, must be receiving goserelin for at least 28 days prior to entering the study and will remain on goserelin throughout the study, in accordance with the prescribing information and according to the study site's standard practice. The schedule for administration of goserelin for each individual participant is decoupled from the rest of the study visit schedule, and will be determined by the date of the participant's most recent dose of goserelin at the time of study entry (with "goserelin C1D1" defined as the date of the participant's most recent dose + 28 days, then every 28 days subsequently).

All study participants (1L and 2L populations) will receive the Investigator's choice of AI (letrozole) or fulvestrant plus lerociclib 150 mg BID. All participants should be treated according to the best current practice guidelines and standard of care within each institution or country where the study is conducted.

The study will consist of 3 phases: a Screening Phase of up to 42 days in duration; a Treatment Phase (which includes a Safety Follow-up Visit occurring 30 days after the last dose of lerociclib); and a Post-Treatment Follow-up Phase (which includes a Survival Follow-up Phase) that will continue until death, loss of follow-up, withdrawal of consent, or the end of the study (whichever occurs first).

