4.9 Safety Evaluation

All safety summaries and analyses will be based upon the Safety Analysis Set as defined in [Section 4.5](#).

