4.9.1.3 Treatment-emergent Adverse Events (TEAEs)

Treatment-emergent adverse events (TEAEs) will be tabulated and are defined as those adverse events that either start or worsen in severity on or after the date/time of first dose of study treatment through 30 days after end of treatment or the day before initiation of a new antineoplastic treatment, whichever occurs first. Where dates are missing or partially missing, AEs will be assumed to be treatment-emergent, unless there is clear evidence (through comparison of partial dates) to suggest that the adverse event started prior to the first dose of study treatment or after the Post-Treatment Follow-up visit. Partial dates will be imputed per rules outlined in [Appendix 6.2](#).

An overall summary table will be created to present high level TEAE and treatment-related adverse event (TRAE) information. The following will be summarized (presenting the number of participants and number of events) by line of therapy, system organ class (SOC), and preferred term (PT):

- TEAEs
- TRAEs
- Serious TEAEs
- Serious TRAEs
- For each study treatment
 - TEAEs Leading to Drug Discontinuation
 - TEAEs Leading to Drug Reduction
 - TEAEs Leading to Drug Interruption
 - TEAEs Leading to Drug Reduction or Interruption

Additionally, the following summaries presenting the number of participants and number of events will also be created:

- TEAEs by line of therapy and PT
- TEAEs in >10% of participants by line of therapy and PT
- TRAEs by line of therapy and PT
- TEAEs by line of therapy, maximum severity grade, SOC, and PT (number of participants only)

Adverse event summaries will be ordered alphabetically for SOC, and decreasing frequency of PT within SOC for the total column (including both lines of therapy).

For each participant and each adverse event, the worst severity recorded will be attributed and used in the by-severity summaries. Similarly, the worst causality (most related to Lerociclib) will be attributed and used in the by-causality summaries. If severity or causality is missing, a conservative approach for AE assessment (implementing the worst case) will be followed.

Adverse events of special interest (AESIs) TEAEs and TRAEs will also be summarized by line of therapy, maximum severity grade, SOC, and PT for the following terms:

| AESI | Definition |
|---------------------------|-----------------------|
| Febrile neutropenia | MedDRA code #10016288 |
| Pneumonitis | MedDRA code #10035742 |

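### By default, the SAP's per-drug tables of TEAEs leading to discontinuation or interruption divide by the whole Safety Analysis Set in each line, so percentages for letrozole, fulvestrant and goserelin are diluted by participants who never received the drug.

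*SAP*

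**What the plan says.** **Which tables.** SAP 4.9.1.3 lists a block of summaries to be made for each study treatment, by line of therapy, SOC and PT. It includes "TEAEs Leading to Drug Discontinuation", with parallel tables for interruption, reduction, and the two combined.

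**Which denominator.** SAP 4.9.1.3 asks for numbers of participants and events and says nothing about a denominator. The general rule in SAP 4.2.4 opens "Unless otherwise specified for a given analysis, categorical data will be presented by the following rules". It then uses adverse events as its example: "Categorical data not broken out by time (e.g., AE incidence) will be summarized in terms of the number of participants in the appropriate analysis set", labelled n. The rule for percentages is "Percentages will be calculated using n as the denominator as described above".

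**Which analysis set.** SAP 4.9 states "All safety summaries and analyses will be based upon the Safety Analysis Set". SAP 4.5 and protocol 9.2 define that set as enrolled participants with at least one dose of any IMP or NIMP. Neither section defines a drug-specific set.

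**Who receives which drug.** Under protocol 4.1, all participants "will receive the Investigator's choice of AI (letrozole) or fulvestrant plus lerociclib 150 mg BID". Protocol 6.1 presents letrozole and fulvestrant as alternatives and restricts goserelin to pre- or perimenopausal women and men.

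**The concern.** Someone who never received a drug cannot stop or interrupt it. Under the default rule, a participant on fulvestrant still counts in the denominator of the letrozole table and the reverse, and everyone not on goserelin counts in the goserelin table.

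A table headed with one drug's name will be read as that drug's discontinuation or interruption rate. On the default denominator it is a product of two things: how often exposed participants had the event, and how many participants were given the drug. The second is the investigator's choice for letrozole and fulvestrant, and menopausal status and sex for goserelin.

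The study is descriptive (protocol 9.1) and its primary objective is the safety and tolerability of the combination. The printed percentages are therefore the result, and no later model or test would correct them.

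**Working it through.** **Inputs.**
- About 50 participants per line and 100 in total (protocol 9.4, SAP 4.12).
- Letrozole or fulvestrant, one per participant (protocol 4.1, 6.1). The split by line is not stated, so it is assumed below.
- Goserelin for a subset only (protocol 6.1). The share is not stated, so it is assumed below.

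**The plan's own figure.** The only precision statement concerns ORR: 0.8 × 50 = 40 participants with measurable disease per line, with a 95% CI half-width of at most about 16%. At n = 40 the largest Clopper-Pearson half-width is 16.2% (20 responders) and the Wald value at 50% is 15.5%, so it reproduces. The present point uses only the 50 per line from it.

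**Formula.** Let x be the participants with a TEAE leading to discontinuation of a given drug, m those in the line who received that drug, and N the Safety Analysis Set in the line.
- Shown under the default rule: x/N.
- Rate among exposed participants: x/m.
- Ratio of shown to exposed rate: (x/N) ÷ (x/m) = m/N, the drug's exposure share. The understatement is 1 − m/N.

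**Bound for letrozole and fulvestrant.** If nobody receives both, the two counts sum to at most N, so the smaller is at most N/2. In a line of 50 that is 25/50 = 0.50, and in the total column 50/100 = 0.50. The less-used drug is then shown at no more than half its rate among exposed participants.

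**Illustration, N = 50 and x = 2 on the less-used drug (splits assumed).** The default rule shows 2/50 = 4.0% (exact 95% CI 0.5 to 13.7) for every split.

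| Assumed split | Among exposed | Exact 95% CI (%) | Understated by |
|---|---|---|---|
| 25:25 | 2/25 = 8.0% | 1.0 to 26.0 | 50% |
| 20:30 | 2/20 = 10.0% | 1.2 to 31.7 | 60% |
| 10:40 | 2/10 = 20.0% | 2.5 to 55.6 | 80% |
| 5:45 | 2/5 = 40.0% | 5.3 to 85.3 | 90% |

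**Goserelin (shares assumed).** Use by 10%, 30%, 50% or 60% of a line gives an understatement of 90%, 70%, 50% or 40%.

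**If some participants receive both drugs.** With a proportion c on both, the two shares sum to at most 1 + c, so the smaller is at most (1 + c)/2. At c = 10% the bound moves from 0.50 to 0.55. The documents describe no switching.

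**The case against.** **The denominator is inferred.** SAP 4.9.1.3 mentions only counts, the table shells are not in the documents, and SAP 4.2.4 allows exceptions and speaks of the appropriate analysis set. This stands in part: the SAP never says outright that the letrozole table divides by everyone. But SAP 4.2.4 names AE incidence, SAP 4.5 and 4.9 assign all safety analyses to one set, and 4.9.1.3 specifies no exception. A programmer following the text would use the whole set.

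**Dividing by everyone is legitimate.** The proportion of all treated participants who stopped letrozole because of an AE correctly describes the regimen population. This stands, so understated here means relative to participants exposed to the drug. It does not rescue a table presented drug by drug.

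**Readers can recover the right figure.** Counts are shown, and SAP 4.8 summarizes compliance for each treatment, so the numbers on letrozole and fulvestrant should be visible there. This is fair for those two drugs. It fails for goserelin, whose compliance is not calculated. The exposure variables in SAP 4.9.5 are for lerociclib, and the disposition table in SAP 4.4.1 counts any study medication.

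**The consequence is limited.** No test or decision rule uses these percentages, and protocol 6.5.2 allows no dose modification of the endocrine drugs, so their reduction tables should be nearly empty. Both points stand; discontinuation and interruption are what matter.

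**Stronger readings to avoid.** A reader might infer that one endocrine drug is understated by half in every line whatever the mix. That does not follow: a line using only one of the two drugs has no dilution for that drug and no rate to dilute for the other. A reader might also infer that second-line participants will mostly get fulvestrant, so their letrozole rate is diluted most. The documents leave the choice to the investigator, admit second-line participants after tamoxifen as well as an aromatase inhibitor, and give no split.

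**Conclusion.** The point holds for the background endocrine drugs. Followed as written, the SAP gives percentages for discontinuation and interruption of letrozole, fulvestrant and goserelin that equal the rate among exposed participants times the exposure share.

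The factor of one half for the less-used of letrozole and fulvestrant rests on three conditions: both are used in the line, at least one event occurs on the less-used drug, and nobody receives both. The size for goserelin is 1 minus a share the documents do not state. Any distortion between the first-line and second-line columns depends on an assumed prescribing mix, and the SAP plans no formal comparison between them.

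It would be wrong to conclude that the primary safety results are compromised. The overall TEAE and SAE tables use the right denominator, and the lerociclib tables are essentially unaffected because nearly everyone in the Safety Analysis Set receives lerociclib. This should be corrected, but it is confined to the endocrine-drug tables.

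**What to change.** Add to SAP 4.9.1.3: *For summaries by study treatment, the denominator is the number of participants in the Safety Analysis Set, within line of therapy, who received at least one dose of that treatment.* Print that N in each column header, and apply the same rule to the total column across lines.

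The cost is one SAP sentence and a change to the table shells. No new data are needed, because SAP 4.8 already records administration dates for each treatment. The downside is small denominators for less-used drugs: 2 of 10 has an exact 95% CI of 2.5 to 55.6%. That imprecision exists anyway, and the printed N makes it visible.

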4.2.5 Time-to-event Data

Descriptive summaries of time-to-event data will include median, twenty-fifth and seventy-fifth percentiles, and 95% confidence intervals (CIs) (where applicable) based on Kaplan-Meier methods.

4.3 Software

All report outputs will be produced using SAS® version 9.4 [2] or a later version in a secure and validated environment.

4.4 Study Participants

4.4.1 Disposition of Participants

A clear accounting of the disposition of all participants who enter the study will be summarized, from screening to study completion, including the following:

- The number of participants screened for entry into the study
- The number and percentage of participants excluded prior to first treatment
- The number and percentage of participants treated (with at least one dose of study medication)
- The number and percentage of participants in each analysis population
- The number and percentage of participants withdrawing from study treatment with primary reason
- The number and percentage of participants withdrawing from the study with primary reason

A by-participant listing of eligibility details will be produced, including visit dates, cycle numbers, date of withdrawal from treatment, date of withdrawal from study (including reason for discontinuation from treatment/study and duration of treatment/study participation).

4.4.2 Protocol Deviations

Major protocol deviations are defined as a subset of protocol deviations that may significantly impact the completeness, accuracy, and/or reliability of the study data or that may significantly affect a participant's rights, safety, or well-being. All major protocol deviations will be categorized and

summarized descriptively, as per data collected by protocol deviation tracking database. Protocol deviations will be presented for each participant in a by-participant data listing.

Prior to database lock, all protocol deviations will be reviewed and assigned a status of Major Deviation based on clinical or study judgement on their possible impact on study outcomes. As these data are not collected in CRF, if data format is not suitable for summary, only a data listing will be provided.

Protocol deviations and major protocol deviations will be categorized as noted in the Protocol Management Plan.

4.5 Analysis Sets

The following analysis populations will be used for presentation and analysis of data:

- Safety Analysis Set is defined as all enrolled participants who have received at least 1 dose of study intervention (IMP or NIMP).
- Full Analysis Set (FAS) is defined as all enrolled participants who were exposed to lerociclib (IMP) during the study.
- Response Evaluable (RE) Analysis Set is defined as all enrolled participants who were exposed to lerociclib during the study and who had measurable disease at baseline.

All safety analyses will be assessed using the Safety Analysis Set. PFS, OS and QoL will be assessed using the FAS. Tumor response endpoints will be assessed using the RE Analysis Set. As all participants are to receive the same treatment, all analyses will be summarized based on the planned treatment dose. Any deviations from planned treatment will be documented.

The FAS and Safety Analysis Set will be derived programmatically using study drug exposure data. The RE Analysis Set will be derived programmatically as determined by investigator assessment of baseline disease status using RECIST v1.1..

A summary of the number and percentage of participants by line of therapy for each analysis set will be presented.

A by-participant listing of analysis set details will be provided, including site, participant identifier, inclusion/exclusion flag for each set, and reason for exclusion from each set..

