The study will consist of 3 phases: a Screening Phase of up to 42 days in duration; a Treatment Phase (which includes a Safety Follow-up Visit occurring 30 days after the last dose of lerociclib); and a Post-Treatment Follow-up Phase (which includes a Survival Follow-up Phase) that will continue until participant death, loss of follow-up, withdrawal of consent, or the end of the overall study (whichever occurs first).

While receiving lerociclib, participants will undergo imaging assessments (via computed tomography [CT] of the chest/abdomen/pelvis with contrast or magnetic resonance imaging [MRI] with gadolinium) every 8 weeks for the first 12 months, then every 12 weeks thereafter. All participants will undergo a bone scan at baseline and annually thereafter (or as per the Investigator's standard of care).

If bone disease is identified, participants will require whole-body bone scans every 8 weeks for the first 12 months, then every 12 weeks thereafter.

Optional imaging modalities include a brain CT/MRI (if brain lesion[s] present at Screening), CT/MRI for any disease outside the chest/abdomen/pelvis (if lesion[s] identified at Screening), and/or skin color photography (if skin lesion[s] identified at Screening) every 8 weeks during the first 12 months, then every 12 weeks thereafter.

Number of Participants:

Approximately 100 participants will be enrolled and dosed in this study, with approximately 50 participants enrolled and dosed for each line of therapy (1L or 2L).

Intervention Groups and Duration:

Lerociclib is administered as a 150-mg tablet, to be taken orally twice daily (BID).

Based on current available data, lerociclib may be administered without regard to food; however, dosing under fed conditions appeared to improve gastrointestinal tolerability.

For this reason, as well as for consistency across the study population, participants in this study will be advised to take lerociclib after eating.

All participants (1L and 2L populations) will receive an AI (letrozole) or fulvestrant plus lerociclib 150 mg BID. All participants should be treated according to the best current practice guidelines and standard of care within each institution or country where the study is conducted.

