9.3.1. General Considerations

Descriptive summaries for categorical variables will include counts and percentages. Descriptive summaries for continuous variables will include means, medians, standard deviations, and minimum and maximum values. Descriptive summaries of time-to-event data will include median, 25th and 75th percentiles, and 95% CIs (where applicable) based on Kaplan-Meier methods. All analyses will be performed by line of therapy.

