9.3.2.1. Analysis of Adverse Events

Adverse event data will be coded by SOC and PT using the current version of the MedDRA. The number and percentage of participants experiencing any TEAE and serious TEAE, overall, and by SOC and PT will be tabulated. Treatment-emergent AEs will also be summarized by severity grade (as assessed by the Investigator per NCI CTCAE v5.0).

Treatment-emergent AEs and SAEs related to treatment (ie, study intervention) will be further summarized by the treatment to which each is attributed (eg, lerociclib, letrozole, fulvestrant, or goserelin). Withdrawals due to AEs will be summarized.

Duration of AEs will be determined and included in the listings, along with action taken and outcome. Adverse events leading to treatment discontinuation will also be listed.

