3.2 Endpoints

The following endpoints will be used to evaluate the efficacy and safety of the study treatment based on the study objectives:

| Objectives | Endpoints |
|---|---|
| Primary | |
| To characterize the safety and tolerability of lerociclib in combination with endocrine therapy in participants with 1L and 2L HR+/HER2- mBC. | 
 Incidence of adverse events (AEs) and serious adverse events (SAEs) |
| Secondary | |

| Objectives | Endpoints |
|---|--|
| To investigate the efficacy of lerociclib in combination with endocrine therapy in participants with 1L and 2L HR+/HER2- mBC by line of therapy. | 
 Objective response rate (ORR), defined as the proportion of participants with a best overall response of complete response (CR) or partial response (PR) according to Response Evaluation Criteria in Solid Tumors version 1.1 (RECIST v1.1) as assessed by Investigator Clinical benefit rate (CBR), defined as the proportion of participants with a best overall response of CR, PR, or stable disease (SD) according to RECIST v1.1 as assessed by Investigator Progression-free survival (PFS), defined as the time from first dose of lerociclib until the date of documented progression of disease (PD) or death, according to RECIST v1.1 as assessed by Investigator Overall survival (OS), defined as the time from the date of first dose of lerociclib to the date of death due to any cause Duration of response (DOR), defined as the time from the date of first documented response until the date of confirmed PD or death, according to RECIST v1.1 as assessed by Investigator Time to response (TTR), defined as the time from first dose of lerociclib until the first documented response (CR or PR) |
| To further characterize the safety and tolerability of lerociclib in combination with endocrine therapy in participants with 1L and 2L HR+/HER2- mBC. | 
 Change from baseline in clinical laboratory parameters (hematology, clinical chemistry, coagulation, fasting lipid panel, and urinalysis) Change from baseline in vital signs and 12-lead electrocardiogram (ECG) parameters Clinically significant findings on physical examination |

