4.9.3 Clinical Laboratory Evaluation

Chemical laboratory assessments include hematology, clinical chemistry, routine urinalysis, and pregnancy testing. The laboratory tests required by the protocol are detailed in Appendix 10.2 of the protocol.

All laboratory assessments will use local laboratories with results reported on the CRF. As such, laboratory assessments will be summarized by the visit in which the assessment was conducted.

For by-visit summaries, visit windowing will be implemented as specified in Section 4.10.1.3. For across visit summaries (e.g., worst post-baseline value), scheduled, unscheduled and repeat assessments will be considered.

All laboratory tests with values considered clinically significantly abnormal during participation in the study or within 30 days after the last dose of study intervention should be repeated until the values return to normal or baseline or are no longer considered clinically significant by the investigator or medical monitor. When there are repeat laboratory tests conducted on samples collected during the same visit, the last non-missing assessment will be summarized.

Laboratory values for hematology and clinical chemistry will be summarized as raw, change from baseline, and maximum change from baseline (for the participant). Descriptive statistics (for non-categorical data) will be presented by line of therapy for both raw values (n, mean, standard deviation, median, minimum, maximum) and changes from baseline.

A summary of the incidence of abnormal, high, or low values will be created by line of therapy and visit. Shift tables will be created for hematology and clinical chemistry parameters for which normal ranges exist. Shift tables for CTCAE grade shifts from baseline to worst post-baseline will also be presented by line of therapy for hematology and clinical chemistry for low and high shifts separately.

For urinalysis, a summary of the incidence of abnormal, high, and low values will be created. Shift tables will not be created for urinalysis.

A separate summary of findings of potential drug induced liver injury (DILI) will be prepared. The number and proportion of participants meeting one or both of the following criteria at any post-treatment visit will be summarized:

- ALT or AST $3 \times$ ULN and total bilirubin $2 \times$ ULN ($> 35\%$ direct bilirubin) or
- ALT or AST $3 \times$ ULN and international normalized ratio (INR) > 1.5 .

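### The SAP omits two protocol-specified safety summaries (related AEs by attributed drug; change from baseline in coagulation and lipids) while declaring no change of method

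*SAP*

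**What the plan says.** **Treatment.** Protocol 4.1 states: "All study participants (1L and 2L populations) will receive the Investigator's choice of AI (letrozole) or fulvestrant plus lerociclib 150 mg BID". Goserelin is added for pre- or perimenopausal women and for men. SAP 4.5, on the basis for reporting, says: "As all participants are to receive the same treatment, all analyses will be summarized based on the planned treatment dose".

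**Related adverse events.** The primary endpoint in SAP 3.2 is "Incidence of adverse events (AEs) and serious adverse events (SAEs"). Under the primary endpoint analysis, Protocol 9.3.2.1 says that related TEAEs and SAEs "will be further summarized by the treatment to which each is attributed (eg, lerociclib, letrozole, fulvestrant, or goserelin"). SAP 4.9.1.3 lists TRAEs and serious TRAEs by line of therapy, SOC and PT. Its only tables produced separately for each study treatment are those of TEAEs leading to discontinuation, reduction, interruption, and reduction or interruption. Causality for each treatment is a column in the by-participant listings. For by-causality summaries, the worst causality is taken as the one most related to lerociclib.

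**Laboratory.** The secondary safety endpoint in SAP 3.2 is change from baseline in five panels: "hematology, clinical chemistry, coagulation, fasting lipid panel, and urinalysis". Protocol 9.3.3.1 tabulates observed values and changes from baseline in clinical laboratory parameters at each visit. SAP 4.9.3 says: "Laboratory values for hematology and clinical chemistry will be summarized as raw, change from baseline, and maximum change from baseline".

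**Declared changes.** SAP 4.13 says that the SAP makes no changes to the protocol's statistical methods.

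**The concern.** The study's purpose is to describe the safety of lerociclib given with endocrine therapy. Protocol Table 2 itself links arthralgia, hot flushes and fatigue to letrozole, fulvestrant and goserelin, so the protocol's breakdown of related events by drug is what lets a reader separate partner-drug effects from lerociclib effects. A programmer who follows SAP 4.9.1.3 would not produce that breakdown.

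Likewise, a programmer who follows SAP 4.9.3 would not produce change-from-baseline tables for two panels named in the endpoint. Because SAP 4.13 reports no changes, neither omission would be flagged in the study report as a departure from the protocol.

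**Working it through.** The plan gives no figure on this point. Its one design figure, an ORR half-width of about 16% with 40 participants per line, reproduces: the exact (Clopper-Pearson) limits for 20/40 are 33.8% and 66.2%, and (66.2 − 33.8)/2 = 16.2%. Nothing below depends on it. The check is mainly a comparison of text.

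**Step 1. Related-event tables**

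| Summary | Protocol 9.3.2.1 | SAP 4.9.1.3 |
|---|---|---|
| TEAEs and serious TEAEs by SOC and PT | required | specified |
| Related TEAEs by attributed drug | required | TRAEs by line, SOC, PT; no drug split |
| Related SAEs by attributed drug | required | serious TRAEs by line, SOC, PT; no drug split |
| TEAEs by action taken, per drug | not required per drug | four tables |
| Causality per drug | covered by the two required rows above | listings only |

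**Step 2. Which drug does TRAE refer to?** The SAP does not say, and two readings are possible.
- Related to any study drug: all attributions are combined, so 0 of 4 drugs have their own related-event tables.
- Related to lerociclib, as the worst-causality rule suggests: 1 of 4 drugs is covered, and letrozole, fulvestrant and goserelin have none.

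Neither reading gives what Protocol 9.3.2.1 asks for.

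**Step 3. Denominator for the missing tables.** SAP 4.2.4 takes the analysis set as the default denominator, about 50 per line. If only k of those 50 receive a given drug, then

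percentage shown = (k/50) × percentage among recipients.

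The documents do not give k, so the following is an assumed range, for an assumed 20% event rate among recipients:

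| k | k/50 | 20% among recipients is shown as | Largest exact 95% half-width among recipients |
|---|---|---|---|
| 10 | 0.2 | 4% | 31.3% |
| 25 | 0.5 | 10% | 20.4% |
| 40 | 0.8 | 16% | 16.2% |
| 50 | 1.0 | 20% | 14.5% |

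The half-width is half of [Beta quantile at 0.975 with parameters (x+1, n−x), minus Beta quantile at 0.025 with (x, n−x+1)], at its largest over x, with n = k. The added tables would be descriptive and imprecise, but they need the right denominator.

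**Step 4. Laboratory panels**

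| Panel in the endpoint | Value and change summary in SAP 4.9.3 | Other coverage |
|---|---|---|
| Hematology | yes | shift tables |
| Clinical chemistry | yes | shift tables |
| Urinalysis | none specified | explicit summary of abnormal, high and low values |
| Coagulation | none specified | INR in the DILI criteria; listings |
| Fasting lipids | none specified | listings |

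A general summary of abnormal, high or low values names no panel and may also take in the last two rows. These panels cannot simply be read as chemistry: Protocol Table 9 and the endpoint in SAP 3.2 both list them separately. Table 9 gives four coagulation entries (prothrombin time/INR, partial thromboplastin time, D-dimer, fibrinogen) and four lipid entries (total cholesterol, low-density lipoprotein, triglycerides, high-density lipoprotein): 4 + 4 = 8 without a change-from-baseline summary.

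**Step 5. Declaration.** Steps 1 and 4 each show a protocol-specified summary that the SAP does not carry over. SAP 4.13 records neither.

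**The case against.** The strongest reply is that these are gaps in descriptive tables and nothing is lost. Per-drug causality is collected and listed, all laboratory values are listed, INR enters the DILI summary, and SAP 4.2.2 lets analyses be added. It is true that the data exist. But a listing is not the summary the protocol specifies, and permission to add an analysis does not plan one.

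Four stronger readings are tempting, and the documents do not support them.

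- *The SAP pools all drugs because it thinks everyone gets the same treatment.* The sentence in SAP 4.5 concerns planned dose and is followed by a promise to document deviations. SAP 3.1.2 names both partners, SAP 4.8 summarises compliance drug by drug, and four TEAE tables are per drug. Removing the sentence would change no table.
- *The lack of a letrozole/fulvestrant split is a departure.* Protocol 9.3.1 says "All analyses will be performed by line of therapy", and SAP 4.2 follows it. A split by partner is a preference.
- *Differences between lines are confounded by partner.* Investigator's choice makes this possible, but the documents give no partner mix by line, and SAP 3.1.2 disclaims formal comparison between populations.
- *Coagulation and lipids are wholly unsummarised, within the primary analysis.* They belong to a secondary endpoint and may get an abnormal-value summary. What is missing is the change from baseline.

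Nor can one say that endocrine effects will inflate the lerociclib TRAE rate. That requires TRAE to mean related to any drug, which the SAP leaves open.

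**Conclusion.** The point holds for two omissions and for the statement in SAP 4.13 that is inconsistent with them. The protocol's breakdown of related TEAEs and SAEs by attributed drug is missing: none or one of four drugs is covered, depending on what TRAE means. No change-from-baseline summary is specified for coagulation or fasting lipids, eight entries in Table 9.

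The consequence is moderate. Overall AE and SAE incidence, the primary endpoint itself, is fully specified. What would be lost is the protocol's further breakdown of it and part of one secondary safety endpoint. No sample size or stated figure is affected.

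This rests on reading the public text of SAP 4.9.1.3 and 4.9.3, where no redaction is visible. The output specifications are not among the documents. If they already contain these tables, the SAP text still needs to match them.

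**What to change.** - **SAP 4.9.1.3:** define TRAE, stating the drug or drugs it refers to and which of the five attribution categories in Protocol Appendix 3 count as related. Add TRAE and serious TRAE tables by attributed drug, within line, with that drug's recipients as denominator. Two event types × four drugs = eight displays, or two tables with drug columns.
- **SAP 4.9.3:** extend the value and change-from-baseline summaries to coagulation and fasting lipids. For urinalysis, state whether the abnormal-value summary is meant to serve as the endpoint analysis.
- **SAP 4.13:** make the statement true, by adding the tables or by declaring and justifying any that are dropped.
- **Optional:** reword the sentence in SAP 4.5 to recognise the two endocrine partners, and add a descriptive AE table by partner. The protocol requires neither.

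The cost is a SAP revision and a few more tables. Causality per treatment and both laboratory panels are already collected, so no new data or change in sample size is needed.
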